Sleep-Disordered Breathing in the Acute Phase after Stroke and Neuropsychiatric Outcomes

2025-01-31

Sleep-Disordered Breathing in the Acute Phase after Stroke and Neuropsychiatric Outcomes

Background/Objectives

Stroke is the second leading cause of death and a common cause of acquired disability worldwide, and the burden of the disease at the societal level is expected to increase in the coming decades (1-4). Stroke can result in various long-term consequences, both neurological (such as aphasia, paresis, sensory or visual disturbances, and coordination and balance disorders) and neuropsychiatric (such as cognitive impairment, depression, and fatigue) (5-8). These consequences, in turn, affect stroke survivors' physical functions, activity levels, and ability to participate in daily activities (9-13).

Post-stroke fatigue is common, with prevalence estimates ranging between 25- 85%, and 40% of stroke survivors have reported it as one of their worst symptoms (14-16). Recent Swedish studies have estimated the long-term prevalence 3-5 years after stroke to be between 24-52% (17, 18). Post-stroke fatigue partially overlaps with post-stroke depression, but approximately 70% of individuals with significant fatigue do not exhibit concurrent depressive symptoms (17). The condition is associated with poorer performance in daily activities and lower health-related quality of life (17). Currently, there are no specific treatments for post-stroke fatigue (19). Due to its high prevalence and consequences, it has recently been identified as one of the top ten priority research questions in stroke rehabilitation by the UK National Institute for Health and Care Research (20).

There are conflicting reports on whether traditional vascular risk factors such as hypertension, hyperlipidemia, heart disease (including atrial fibrillation), and smoking contribute to post-stroke fatigue (21, 22). Obesity is associated with post-stroke fatigue, and sleep-disordered breathing (SDB) has also emerged as a potential risk factor (23).

Sleep-disordered breathing is prevalent after stroke, occurring in 50-70% of some populations (25). The dominant condition is obstructive sleep apnea syndrome (OSAS), followed by central sleep apnea (26). Established treatments for OSAS include continuous positive airway pressure (CPAP), mandibular advancement devices, surgical interventions, and weight loss (26), which can reduce daytime sleepiness. Research is ongoing regarding the extent to which treated OSAS can contribute to secondary prevention in stroke (27). Current American guidelines for secondary prevention provide a class 2b recommendation with moderate evidence for considering OSAS screening after stroke or transient ischemic attack (TIA) (28). The diagnosis is primarily made through overnight respiratory monitoring, with polysomnography being the gold standard, although it is time- and resource-intensive and may be cumbersome for the patient (29). Limited polygraphic examinations can also be conducted both in hospitals and at home (29).

Research Questions:

1. What is the 1-year prevalence of post-stroke fatigue in a hospital-based cohort in Blekinge?
2. How many individuals with stroke have significant sleep-disordered breathing according to non-invasive measurement?
3. What proportion of individuals with post-stroke fatigue had significant sleep-disordered breathing during hospitalization?
4. Can early, non-invasive, and simple measurement of sleep-disordered breathing in hospitals predict a subgroup of stroke patients who will develop significant fatigue?
5. Is there evidence that treatment goals after stroke are achieved to a lesser extent in those with significant fatigue?

By answering these questions, our study aims to: i) Facilitate patient selection for potential future clinical trials, e.g., CPAP treatment for preventing/treating post-stroke fatigue. ii) Identify potential subgroups among individuals with post-stroke fatigue. iii) Investigate risk factors for post-stroke fatigue, including sleep-disordered breathing. iv) Examine whether fatigue leads to poorer adherence to secondary preventive treatment goals (30).

Methodology

The present study has been approved by the Swedish Ethical Review Authority, diary number 2024-02659-01.

Study participants will be prospectively identified at the Department of Medicine, Blekinge Hospital, Karlskrona. Inclusion and exclusion criteria are as follows:

Inclusion criteria:

- Age \geq 18 years
- Stroke according to WHO definition (31) (ischemic stroke, intracerebral hemorrhage, or subarachnoid hemorrhage)
- TIA with MRI-verified lesions corresponding to symptoms
- Informed consent to participate

Exclusion criteria:

- Traumatic stroke
- Tumor-associated bleeding
- Expected survival <3 months
- Unconsciousness (RLS >3)

Potential participants will be identified by medical staff, and informed consent will be obtained by a researcher.

Upon obtaining consent, patients will be equipped with a Withings Sleep Analyzer and a Nonin WristPro 2 pulse oximeter during hospital stay days 1- 3. Withings Sleep Analyzer is validated to detect moderate-severe obstructive sleep apnea (32). The patient is also equipped with a Nonin WristPro 2 pulse oximeter with the possibility to retrospectively obtain registered data regarding nocturnal hypoxia (T90 – time under 90% oxygen saturation, and ODI – oxygen desaturation index).

Baseline data collected include:

- National Institutes of Health Stroke Scale (NIHSS) (33)
- Pre-stroke modified Rankin Scale (mRS) (34)
- Previous stroke history
- BMI
- STOP-BANG questionnaire (35)

If it is not possible to obtain these data, including NIHSS, during the hospital stay, they will be collected later through chart review when possible. During chart review/clinical examination, the following will also be recorded:

- Main subtype of stroke (IS, ICH, SAH)
- Oxfordshire Community Stroke Project classification (OCSP) (36)
- Trial of Org 10172 in acute stroke treatment (TOAST) classification (37)
- Charlson Comorbidity Index (CCI) (38)
- Hypertension (>140/90 mmHg at discharge or antihypertensive treatment in the last 2 weeks)
- Diabetes mellitus (previous diagnosis, fasting blood glucose >6.1 mmol/L, or non-fasting blood glucose >11 mmol/L)
- Heart disease (ischemic heart disease, previous MI, angina, PCI, CABG, heart failure, arrhythmias)
- Hyperlipidemia (previous diagnosis, lipid-lowering treatment, total cholesterol >5 mmol/L, LDL >3 mmol/L)
- Smoking
- COPD (ICD-10 J44 or described in chart)
- Depression diagnosis (ICD F32-33) or antidepressant treatment
- HbA1c, lipid status, blood pressure at discharge
- Medications (antiplatelets, anticoagulants, antidiabetics, antihypertensives, opioids, sedatives, statins, antidepressants) at onset and discharge
- Long-term ECG monitoring
- Carotid stenosis degree on carotid ultrasound exam
- Coagulation assessment, if performed
- Previous stroke/recurrent stroke within 1 year

Participants are subsequently invited via letter for a follow-up visit approximately 1 year after stroke (+3 months, but not earlier than 1 year) at the district nurse students' training clinic at Blekinge Institute of Technology. During this visit, the following will be recorded:

Follow-up assessment (1 year after stroke):

- Fatigue Assessment Scale (FAS) (39)
- Fatigue Visual Analogue Scale (VAFS)
- PHQ-9 depression scale (40)
- mRS (34)
- Blood pressure
- Height, weight, BMI
- Blood tests (HbA1c, lipid profile)
- Smoking
- Medication adherence
- Stroke Impact Scale (41)
- Ongoing BiPAP or CPAP treatment
- Alcohol consumption

Recruitment Calculation

With a confidence level of 0.05, statistical power of 80%, an estimated OSAS prevalence of 50%, and estimated significant fatigue prevalence of 30%, a total cohort of 284 participants is required to detect a doubled relative risk of significant fatigue with OSA. Considering a 10-20% loss to follow-up, approximately 340 participants need to be included.

Ethical Considerations

The project involves non-invasive procedures except for blood sampling at follow-up.

Written informed consent will be obtained.

Data for research purposes such as apnea-hypopnea index and time under 90% blood oxygen saturation are collected outside of clinical praxis and do not in any way hinder concurrent investigation for OSA if clinically indicated. The sleep study data will be interpreted at the 1-year follow-up and the study physicians will decide if further investigation is needed.

Affiliated Researchers

Researcher [name] is the principal investigator, with [name] and [name] as co-investigators.

References

1. GBD 2019 Diseases and Injuries Collaborators. Global burden of 369 diseases and injuries in 204 countries and territories, 1990–2019: a systematic analysis for the Global Burden of Disease Study 2019 *Lancet*. 2020;396:1204–1222. doi:10.1016/S0140-6736(20)30925-9.
2. GBD 2016 DALYs and HALE Collaborators: Global, regional, and national disability-adjusted life-years (DALYs) for 333 diseases and injuries and healthy life expectancy (HALE) for 195 countries and territories, 1990–2016: a systematic analysis for the Global Burden of Disease Study 2016. *Lancet* 2017; 390: 1260– 1344.

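### The 284 participants do not follow from a doubled relative risk; the figure matches a doubled odds ratio (relative risk about 1.54), so the stated effect and power do not belong together

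*Protocol*

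**What the plan says.** The Recruitment Calculation section of the protocol gives its inputs in one sentence: "With a confidence level of 0.05, statistical power of 80"% (the first figure is evidently the significance level), then "an estimated OSAS prevalence of 50%, and estimated significant fatigue prevalence of 30"%. From these it concludes that "a total cohort of 284 participants is required to detect a doubled relative risk of significant fatigue with OSA". Loss to follow-up of 10–20% is applied afterwards to reach about 340, so 284 is the number of evaluable participants and contains no hidden allowance.

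The section does not name a test, a formula or the sidedness. It does not say whether the 30% is the fatigue risk in the whole cohort, in patients without OSA or in patients with OSA. It does not mention an odds ratio.

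**The concern.** With half the cohort exposed and fatigue near 30%, doubling the risk is a large absolute difference: 20 percentage points if 30% is the overall rate, 30 points if it is the rate without OSA. Differences of that size need far fewer than 284 participants.

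This is the protocol's only power statement. It supports the association between sleep-disordered breathing and fatigue that lies behind research question 4 and the third study aim. A reader who takes it at face value will treat a relative risk of 2 as the effect detectable with 80% power, and will judge a null result against that effect. If the intended effect was smaller, such as an odds ratio of 2, the text hides that, and a reader cannot tell whether 284 gives the stated power.

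**Working it through.** **Inputs** (Recruitment Calculation): level 0.05, power 80%, exposure 50% (equal groups), fatigue 30%, relative risk 2. Sidedness is not stated; two-sided is assumed, so z₁ = 1.960, z₂ = 0.842 and (z₁ + z₂)² = 7.849.

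**Formulas**, per group, with p₀ and p₁ the risks without and with OSA, p̄ their mean and d = p₁ − p₀:

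- Pooled: n = [z₁√(2p̄(1−p̄)) + z₂√(p₀(1−p₀) + p₁(1−p₁))]² / d²
- Continuity-corrected: n′ = (n/4)·[1 + √(1 + 4/(n·d))]²
- Kelsey: n = (z₁ + z₂)²·2p̄(1−p̄) / d²

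**Step 1: attempt to reproduce 284 with a relative risk of 2.** Worked case, 30% overall. Equal groups give (p₀ + 2p₀)/2 = 0.30, so p₀ = 0.20 and p₁ = 0.40. The pooled formula gives [1.960·0.6481 + 0.842·0.6325]² / 0.04 = 81.2, so 82 per group and 164 in total.

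| The 30% is the risk | p₀ vs p₁ | Pooled, per group | Total | Total, continuity-corrected | Total, Kelsey |
|---|---|---|---|---|---|
| overall | 0.20 vs 0.40 | 81.2 | 164 | 182 | 166 |
| without OSA | 0.30 vs 0.60 | 42.0 | 84 | 98 | 88 |
| with OSA | 0.15 vs 0.30 | 120.5 | 242 | 268 | 244 |

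Unpooled, log-relative-risk, log-odds-ratio and arcsine versions give 158–180, 80–100 and 236–262 for the three rows. One-sided tests give smaller numbers (128, 66 and 190 by the pooled formula). The closest result at the stated power is 268, which is 16/284 = 5.6% short. Totals near 284 with a relative risk of 2 appear only at another power: 288 at 95% power (20% vs 40%, continuity-corrected), or 288 at 90% power one-sided (15% vs 30%, continuity-corrected).

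**Step 2: try an odds ratio of 2.** With 30% fatigue without OSA, the odds are 0.30/0.70 = 0.4286. Doubled, they are 0.8571, so p₁ = 0.8571/1.8571 = 0.4615. Then d = 0.1615, p̄ = 0.3808 and the relative risk is 0.4615/0.30 = 1.54.

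- Kelsey: 7.849·2·0.3808·0.6192 / 0.1615² = 141.84, so 142 per group and **284 in total**.
- Pooled: 140.7, so 282 in total.
- Continuity-corrected: 306 in total.

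Overall fatigue in this scenario is 38%, not 30%.

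With an odds ratio of 2 and 30% overall, the risks are 0.228 vs 0.372 (relative risk 1.63), and the total is 320 (pooled) or 322 (Kelsey).

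**Step 3: what 284 delivers.** Power = Φ{[d√142 − z₁√(2p̄(1−p̄))] / √(p₀(1−p₀) + p₁(1−p₁))}.

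| Scenario | Power at 284 |
|---|---|
| Relative risk 2, 20% vs 40% | 96.1% |
| Relative risk 2, 30% vs 60% | over 99.9% |
| Relative risk 2, 15% vs 30% | 86.1% |
| Odds ratio 2, 30% vs 46.2% | 80.4% |
| Odds ratio 2, 22.8% vs 37.2% | 75.4% |

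Solving the same expression for 80% power, the smallest detectable relative risk at 284 is 1.68 with 30% overall (22.4% vs 37.6%) and 1.54 with 30% in those without OSA (30% vs 46.1%).

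**The case against.** Three points on the other side deserve weight.

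- **The odds-ratio origin is inferred.** The protocol does not mention an odds ratio. The exact match needs an odds ratio of 2, 30% as the risk without OSA, and the Kelsey formula without continuity correction. This stands as a limit on the explanation. It does not rescue the figure, because 284 fails for a relative risk of 2 whatever its source.
- **The error is conservative for the stated effect.** On every reading of the 30%, 284 gives more than 80% power for a doubled risk. This also stands: the cohort is not underpowered for what the sentence claims. What is wrong is that 284 is presented as the number required, together with the implied 80% power and detection limit. The conservative direction also holds only if a relative risk of 2 was meant. An odds ratio of 2 with 30% overall would leave power at 75%, although the protocol states neither of those two conditions.
- **The practical consequences are modest.** The study is observational, most procedures are non-invasive, and research questions 1–3 concern prevalences and proportions. That limits the harm of oversizing, but not the harm of a misstated detectable effect for research question 4.

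A covariate allowance or other design detail could in principle explain a larger number. The protocol mentions none, and its sentence ties 284 directly to the listed inputs.

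**Conclusion.** The concern holds. For an unadjusted comparison of two equal groups at a two-sided 0.05 level and 80% power, 284 is not the size for a relative risk of 2 on any reading of the 30%. The stated number exceeds the requirement by 102–120 participants if 30% is the overall prevalence (284 − 182 and 284 − 164), by 186–200 if it is the risk without OSA (284 − 98 and 284 − 84), and by 16–42 on the least natural reading, the risk with OSA (284 − 268 and 284 − 242).

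The figure is consistent with an odds ratio of 2 from 30% without OSA, a relative risk of about 1.54. The number, the effect and the power printed in the protocol are therefore incompatible, and this must be corrected because it is the only planning figure given.

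The conclusion assumes a two-sided test and OSA in exactly half the cohort. A one-sided test widens the gap for a relative risk of 2.

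**What to change.** The recruitment target can stay; the paragraph should be restated. The sponsor should first confirm which effect measure was intended and to which group the 30% applies, then give both group risks, the formula and the sidedness, and call 0.05 a significance level.

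- **If an odds ratio of 2 with 30% fatigue without OSA was intended:** *284 evaluable participants give 80% power (two-sided significance level 0.05) to detect an odds ratio of 2.0, that is 30% fatigue without OSA versus 46% with OSA (relative risk 1.54), with OSA in 50%.* This statement is true of 284 participants whichever target was meant.
- **If a relative risk of 2 with 30% fatigue overall was intended:** state that about 164 evaluable participants are needed (182 with continuity correction), that 284 gives 96% power, and that the relative risk detectable with 80% power is about 1.7.
- **If an odds ratio of 2 with 30% fatigue overall was intended:** state that 284 gives 75% power, or plan for about 320 evaluable participants.

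The first two cases cost one reworded paragraph and no additional participants. Only the third, if 80% power is to be kept, raises the required number.

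### The enrolment figure of about 340 keeps the required 284 only up to about 16.5% loss to follow-up; at the stated upper limit of 20%, 272 remain.

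*Protocol*

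**What the plan says.** The point lies within the Protocol's Recruitment Calculation section. The design inputs are "With a confidence level of 0.05, statistical power of 80" per cent, "an estimated OSAS prevalence of 50" per cent and "estimated significant fatigue prevalence of 30" per cent. From these the section concludes that "a total cohort of 284 participants is required to detect a doubled relative risk of significant fatigue with OSA". The next sentence turns that requirement into an enrolment figure: "Considering a 10-20% loss to follow-up, approximately 340 participants need to be included".

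The section does not say how the allowance was calculated, or which loss rate between 10% and 20% the figure of 340 is meant to absorb.

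**The concern.** The section puts a fixed requirement (284), a loss range with an upper limit (20%) and one enrolment figure (340) next to each other, with no qualification. The natural reading is that 340 enrolled will still yield 284 wherever loss falls in that range. It does not in roughly the top third.

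What is at stake is modest but practical. Under the Methodology section, fatigue is assessed at a visit between 1 year and 1 year plus 3 months after stroke, to which participants are invited by letter. The only survival-related exclusion is expected survival under 3 months, so later deaths as well as non-attendance reduce the number analysed. Investigators watching attrition would believe they are safe up to 20% when the margin against their own requirement ends at about 16.5%.

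**Working it through.** **Inputs, all from the Recruitment Calculation:** required number 284; loss to follow-up d = 10% to 20%; enrolment about 340.

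**1. Where 340 could come from.**
- Dividing by the retained fraction at the middle of the range: 284 / 0.85 = 334.1, so 335, which could be rounded up to about 340.
- Multiplying up at the top of the range: 284 × 1.2 = 340.8.
- Dividing at the top of the range: 284 / 0.80 = 355, which does not match.

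The first two both fit, so the text does not settle which was used.

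**2. Enrolment needed, 284 / (1 − d), and number retained, 340 × (1 − d).**

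| Loss d | Enrolment needed to keep 284 | Retained from 340 | Against 284 |
|---|---|---|---|
| 10% | 315.6 → 316 | 306 | +22 |
| 15% | 334.1 → 335 | 289 | +5 |
| 16% | 338.1 → 339 | 285.6 → 285 | +1 |
| 17% | 342.2 → 343 | 282.2 → 282 | −2 |
| 20% | 355 | 272 | −12 |

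**3. Break-even.** (340 − 284) / 340 = 56 / 340 = 16.5%. The uncovered stretch from 16.5% to 20% is 3.5 of the 10 percentage points stated.

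**4. Shortfall at 20%.** 284 − 272 = 12, and 12 / 284 = 4.2%.

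**5. Effect on power.** The protocol gives no risks by group, so every pair below is an assumption. The calculation uses the pooled two-proportion formula, two-sided 0.05 (sidedness is also assumed), and equal groups from the stated 50% prevalence. With n = N/2 per group and p̄ the mean of p₁ and p₂:

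power = Φ{ [ |p₁ − p₂|√n − 1.96√(2p̄(1 − p̄)) ] / √(p₁(1 − p₁) + p₂(1 − p₂)) }

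| Assumed risks | Relative risk | Power at 284 | Power at 272 |
|---|---|---|---|
| 15% v 30% | 2 | 0.861 | 0.846 |
| 20% v 40% | 2 | 0.961 | 0.953 |
| 30% v 60% | 2 | 0.9995 | 0.9992 |
| 30% v 46% | about 1.5 | 0.796 | 0.779 |
| 30% v 46.15% | about 1.5 | 0.804 | 0.787 |

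For the stated relative risk of 2, losing 12 participants leaves power above 80% in each scenario tried. In the last two rows the loss costs about 1.7 percentage points and takes power slightly below 80%.

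**The case against.** The strongest reply is that nothing false has been said. The sentence offers an approximate number for a range. It can be read as a mid-range planning value: at 15% the need is 335, and 340 leaves 289. On that reading what is missing is a stated tolerance, and no calculation error is shown. This stands in part. The derivation of 340 is unknown, so a multiply-instead-of-divide slip cannot be claimed. But the sentence does not confine 340 to 15% loss, and rounding does not stretch 340 to 355.

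A second reply is that the consequence is negligible: 12 people, only above 16.5% loss, with no loss of adequate power for a relative risk of 2. That is right, and it is why the point is minor.

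A third reply is that the benchmark of 284 is itself uncertain. Under the same formula, a relative risk of 2 at 80% power needs 242 (15% v 30%), 164 (20% v 40%) or 84 (30% v 60%), and 272 exceeds all three. Of the scenarios with 30% risk in the unexposed, the one close to 284 is 30% v 46.15%, which is an odds ratio of 2 and needs 282. This is a fair observation, and it means the reassuring power figures come from scenarios that do not generate 284. It does not remove the point, which is that 340 misses the protocol's own stated requirement in part of its own stated range.

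**Conclusion.** The concern holds as a minor point. An enrolment of 340 satisfies the protocol's requirement of 284 up to about 16.5% loss and fails it above that, by 12 participants (4.2%) at 20%. This rests only on the three figures in the Recruitment Calculation and on treating 284 as the number needed at follow-up.

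It does not show that the study is underpowered. Under the assumed risks with a relative risk of 2, power at 272 is between 0.846 and 0.999. It drops to 0.78-0.79 only if 284 was built on about 30% v 46%, which the protocol does not state. Nor does it show how 340 was reached.

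**What to change.** Replace the allowance sentence with one that states its tolerance, for example: 340 enrolled yields at least 284 evaluable participants if loss to follow-up is at most 16%; at 20% loss about 272 remain.

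The wording is correct however 340 was derived. It costs one sentence and a slightly less favourable stated margin. No added enrolment and no change of procedure are needed.

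### Does reading the sleep recordings at the 1-year follow-up, with no stated order relative to the fatigue scales, put the SDB–fatigue association at risk?

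*Protocol*

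**What the plan says.** The exposure is recorded in hospital on days 1–3 by an under-mattress analyser and a wrist oximeter. The Methodology describes the oximeter as coming "with the possibility to retrospectively obtain registered data regarding nocturnal hypoxia".

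The outcome is collected at a visit about a year later. The protocol introduces the visit items with "During this visit, the following will be recorded", and FAS and VAFS head the list. The same list includes "Ongoing BiPAP or CPAP treatment".

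Ethical Considerations contains the only statement on when the recordings are read: "The sleep study data will be interpreted at the 1-year follow-up". The sentence goes on to say that "the study physicians will decide if further investigation is needed". Just before it, the protocol says that the research data "do not in any way hinder concurrent investigation for OSA if clinically indicated".

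The questions that depend on both measurements are Research Questions 3 ("What proportion of individuals with post-stroke fatigue had significant sleep-disordered breathing during hospitalization") and 4 ("Can early, non-invasive, and simple measurement of sleep-disordered breathing in hospitals predict a subgroup of stroke patients who will develop significant fatigue").

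**The concern.** The exposure is interpreted at the same named time point at which a self-rated outcome is obtained, with no order and no masking stated. Two routes to bias can be imagined.

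- **Disclosure.** If the recording is opened first and the participant hears that it suggests sleep apnoea, the fatigue ratings that follow may drift upwards. That would create or inflate the association behind Research Questions 3 and 4. Visit order is a matter of conduct, normally not fixed in a SAP, and a rating given after disclosure cannot be repaired in analysis.
- **Classification.** If fatigue is rated first, whoever reads the recording may know the answer. Borderline recordings could then be called significant more often in fatigued participants. The protocol gives no numeric threshold for significant SDB.

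For any one participant these are alternatives, so their effects do not add up.

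**Working it through.** **What the text supports.** Three facts hold: interpretation is placed at the 1-year follow-up, the fatigue scales are collected there, and no order is given. Three others limit what can be built on them.

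1. The sentence sits under Ethical Considerations and is tied to a decision on further investigation. It may name a time point rather than an event inside the visit.
2. The visit is held at a training clinic for district nurse students. Its item list has no sleep-result review, no feedback to the participant and no physician consultation.
3. AHI, ODI and T90 are numeric. A rule-based SDB category can be derived from the stored values at any time, whether or not fatigue is known.

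**Size of the disclosure route.** The protocol gives no figure for this bias, so there is none to reproduce. From Recruitment Calculation I take 30% fatigue, 50% SDB prevalence and 284 participants (142 with SDB, 142 without), used only to set the scale. I assume no true association, so both groups start at 30%. Two further quantities are assumptions without a source in the protocol:

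- x = share of non-fatigued SDB participants who cross the fatigue threshold once told: 2%, 5% or 10%;
- t = share of SDB participants who learn their result at the follow-up before rating fatigue.

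Then P(fatigue | SDB) = 0.30 + 0.70 · x · t, P(fatigue | no SDB) = 0.30, and RR is their ratio. The number of people shifted is 142 × 0.70 × x · t. Rejection is for a pooled two-proportion z-test, two-sided 5%, 142 per group, normal approximation.

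| t | x | P(fatigue given SDB) | RR | People shifted | Rejection |
|---|---|---|---|---|---|
| 100% | 2% | 31.4% | 1.05 | 2.0 | 5.7% |
| 100% | 5% | 33.5% | 1.12 | 5.0 | 9.7% |
| 100% | 10% | 37.0% | 1.23 | 9.9 | 23.9% |
| 80% | 2% | 31.1% | 1.04 | 1.6 | 5.5% |
| 80% | 5% | 32.8% | 1.09 | 4.0 | 8.0% |
| 80% | 10% | 35.6% | 1.19 | 8.0 | 17.1% |
| 25% | 2% | 30.4% | 1.01 | 0.5 | 5.0% |
| 25% | 5% | 30.9% | 1.03 | 1.2 | 5.3% |
| 25% | 10% | 31.8% | 1.06 | 2.5 | 6.2% |
| 0% | any | 30.0% | 1.00 | 0 | 5.0% |

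The 80% rows describe a study in which 20% of SDB participants already know their status from clinical work-up and all the others are told first. At t = 10% the RR is at most 0.307 / 0.30 = 1.02.

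The one figure that would worry an analyst, 23.9%, needs universal disclosure before the questionnaires together with 10% crossing. The protocol describes neither.

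**Size of the classification route.** Let b be the share of borderline recordings (assumed 5%, 10% or 20%), called SDB in 70% of fatigued and 50% of non-fatigued participants (assumed). With s = (1 − b)/2,

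P(fatigue | SDB) = 0.3(s + 0.7b) / [0.3(s + 0.7b) + 0.7(s + 0.5b)],

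and for no SDB the 0.7b in the fatigued terms becomes 0.3b.

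- b = 5%: 30.4% v 29.6%, RR 1.03, rejection 5.3%
- b = 10%: 30.8% v 29.2%, RR 1.06, rejection 6.1%
- b = 20%: 31.6% v 28.3%, RR 1.12, rejection about 9.4%

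This presumes a subjective reading that the protocol does not describe. A fixed numeric rule makes it zero.

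**The case for a change.** The best case for acting is that order is conduct, so the protocol is the place to fix it, and the protocol did choose to state when the recordings are read. Disclosure at the follow-up is plausible because the reading leads to a decision about further investigation. About ten shifted self-ratings would raise the false-positive rate from 5% to about 24%. One sentence requiring that FAS and VAFS be completed before any study sleep result is opened or discussed would close the route, with no effect on sample size, alpha or power.

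Much of this stands: the order is indeed open, the remedy is cheap, and a study team could adopt it in its visit instructions. What does not stand is the step from an unstated order to a flaw. Nothing says or implies that results are given before the questionnaires, and the large figure depends on telling everyone. Leaving the recordings unread until a year has passed is itself the main safeguard, since it keeps the study's own result from participants and staff throughout the interval. Nor would a fixed order give full masking, because participants investigated clinically for sleep apnoea or treated with CPAP or BiPAP may know their status anyway. A companion rule that SDB be categorised without reference to fatigue is an analysis definition that a SAP would ordinarily carry.

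**Conclusion.** No change to the plan is needed. The protocol leaves an order unstated; it neither states a wrong one nor contradicts itself. Followed as written, with exposure recorded by device on hospital days 1–3 and scales self-rated a year later at a visit that lists no sleep review, it leads to no demonstrable wrong result.

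Under a true null and the planning figures, the disclosure route gives RR 1.00 if nobody is told first, 1.01–1.06 if a quarter are, and 1.05–1.23 only if all are. The classification route gives 1.03–1.12 under subjective reading and nothing under a numeric rule. All are small beside the planned RR of 2. These sizes rest on assumed values for the share told, the share who cross the threshold and the share of borderline recordings; the protocol supplies none of them. The conclusion would differ if results were in fact routinely given to participants before the fatigue scales, and nothing in the protocol indicates that.
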